5.6.8 Statistical/Analytical Issues

5.6.8.1 Adjustments for Covariates

No adjustments for covariates are planned.

5.6.8.2 Handling of Dropouts or Missing Data

Reduction in MBL at 12 Months

Missing 12-month menstrual blood loss data will be imputed using last observation carried forward (LOCF). Subjects which undergo surgical reintervention to manage fibroid symptoms prior to 12 months will be excluded from the Reduction in Menstrual Blood Loss analysis.

Surgical Reintervention for HMB due to Treatment Failure at 12 Months

Life-Table methods will be used to calculate the success rate and 95% confidence interval for the rate of surgical reintervention during 12 months. Therefore, subjects that are discontinued prior to 12 months for reasons other than surgical reintervention will be considered censored.

Sensitivity Analyses

Sensitivity analyses will also be conducted to examine the impact of missing data. A worst-case analysis (all missing data imputed as failures) and best-case analysis (all missing data imputed as successes) will be performed. In addition, a tipping point analysis will be performed.

Secondary Endpoint Analyses

No imputations will be made for missing secondary endpoint data.

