10.6 Subject Discontinuation or Withdrawal

- A. Subjects may be involuntarily removed from the study for failure to adhere to the protocol, failure to attend follow-up visits, or due to safety reasons. In such cases, the Investigator shall arrange for an exit visit and complete a study exit case report form for the subject.
- B. Subjects may voluntarily withdraw from the study at any time without reason. The Investigator shall make an effort to obtain an exit visit but cannot insist on the visit if the subject does not wish to come in. The Investigator shall complete a study exit case report form with as much information as is available at the time of withdrawal.
- C. In cases of early termination, as many of the month 12 study procedures should be performed as possible at the time of withdrawal. All information relative to the withdrawal must be fully documented in the subject chart.
- D. If the subject requires removal from the study due to medical reasons (i.e. adverse event) or reasons related to the procedure, the site staff should contact the Gynesonics Medical Director. Adverse device effects that are ongoing at the time of withdrawal will be reported and followed up to 6 weeks following the study treatment or until the adverse device effect resolves or is considered stable, whichever comes last, unless the subject has withdrawn consent for any such follow-up. In such cases, the final follow-up can be either a telephone contact or an office visit.
- E. A subject will be withdrawn from the study if, subsequent to enrollment, she is diagnosed with any condition that could affect menstrual bleeding volume, or if she becomes pregnant at any time following Sonata treatment. In the case of pregnancy, the Investigator and study coordinator should make every attempt to obtain basic pregnancy outcome information and complete the applicable case report form.
- F. A subject may be withdrawn after enrollment and before receiving the study treatment if, at the Investigator's discretion, she has developed a general health condition that would increase risks from study treatment

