Moderate	Surgery lasting less than 30 minutes in patients with additional risk factors; surgery lasting less than 30 minutes in patients aged 40–60 years with no additional risk factors; major surgery in patients younger than 40 years with no additional risk factors	Low-dose unfractionated heparin (5,000 units every 12 hours), low molecular weight heparin (2,500 units dalteparin or 40 mg enoxaparin daily), graduated compression stockings, or intermittent pneumatic compression device
High	Surgery lasting less than 30 minutes in patients older than 60 years or with additional risk factors; major surgery in patients older than 40 years or with additional risk factors	Low-dose unfractionated heparin (5,000 units every 8 hours), low molecular weight heparin (5,000 units dalteparin or 40 mg enoxaparin daily), or intermittent pneumatic compression device
Highest	Major surgery in patients older than 60 years plus prior venous thromboembolism, cancer, or molecular hypercoagulable state	Low-dose unfractionated heparin (5,000 units every 8 hours), low molecular weight heparin (5,000 units dalteparin or 40 mg enoxaparin daily), or intermittent pneumatic compression device/graduated compression stockings + low-dose unfractionated heparin or low molecular weight heparin Consider continuing prophylaxis for 2–4 weeks after discharge.

Modified from Geerts WH, Pineo GF, Helt JA, Bergqvist D, Lassen MR, Colwell CW, et al. Prevention of venous thromboembolism: the Seventh ACCP Conference on Antithrombotic and Thrombolytic Therapy. Chest 2004;126(suppl):338S–400S.

E. Sonata Treatment

- 1) The treatment shall be performed in accordance with the physician Instructions for Use. Highlights are provided below.
 - (a) The intent is for all clinically relevant fibroids to be ablated during a single treatment session.
 - (b) Coincidental removal of an intrauterine polyp up to a maximum diameter of 1.5 cm and type 0 fibroids < 1.0 cm is allowed.
 - (c) A small number of sponsor representatives (generally one to three individuals) may be present during the procedure to provide equipment support if needed as well as for proctoring and general observation.
- 2) **Treatment and Recovery Assessments**
The following data will be collected on the day of the treatment prior to discharge:
 - (a) Treatment location (e.g. ambulatory care center, operating room, etc.)

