5.6 Statistical Methods

All statistical processing will be performed using SAS® unless otherwise stated.

Continuous variables will be summarized descriptively using number of subjects (n), mean, standard deviation (SD), minimum, median, and maximum. Categorical variables will be summarized descriptively using frequency counts and percentages.

Analyses presented for the Full Analysis Set¹ (FAS) will be considered primary. Analyses performed on the Per-Protocol (PP) will be secondary and supportive.

¹ International Conference on Harmonization (ICH) – E9 Statistical Principles for Clinical Trials

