5.6.1 Analysis Populations

The FAS population will be comprised of all study subjects who were treated and who do not meet any of the following criteria:

- Become pregnant during the 12-month post-procedure study period;
- Are diagnosed with a medical condition that would make assessment of menstrual bleeding invalid or unreliable.

The safety population will be comprised of subjects who were treated and have post-baseline information.

The per-protocol (PP) population will include subjects who complete 12 months of follow-up without study protocol violations. The PP population will include subjects from the FAS population who do not meet any of the following criteria:

- Violated the inclusion/exclusion criteria;
- Did not complete a 12 month PBAC;
- Are associated with protocol violations that are considered to influence the endpoint under evaluation;

Subjects who discontinue the study due to a device/procedure-related adverse event (AE) or documented lack of efficacy (without surgical reintervention) will be included in the PP population, with missing data imputed as failure for the 12-month menstrual blood loss (MBL) endpoint.

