6. INDEX OF PLANNED END-OF-TEXT TABLES

Table 14.0.1.1: Summary of Subject Enrollment and Evaluability

Table 14.0.1.2: Summary of Subject Enrollment and Evaluability by Investigator

Table 14.0.2: Summary of Subjects Excluded from Analyses

Table 14.0.3: Summary of Subject Completion/Discontinuation

Table 14.1.1.1: Summary of Subject Demographic Characteristics (Full Analysis Set Subjects)

Table 14.1.1.2: Summary of Subject Demographic Characteristics (Safety Subjects)

Table 14.1.1.3: Summary of Subject Demographic Characteristics (Per-Protocol Subjects)

Table 14.1.2.1: Summary of Subject Baseline Characteristics (Full Analysis Set Subjects)

Table 14.1.2.2: Summary of Subject Baseline Characteristics (Safety Subjects)

Table 14.1.2.3: Summary of Subject Baseline Characteristics (Per-Protocol Subjects)

Table 14.2.1.1: Summary of Efficacy by Evaluation – Primary Efficacy Variables (Full Analysis Set Subjects)

Table 14.2.1.2: Summary of Efficacy by Evaluation – Primary Efficacy Variables (Per-Protocol Subjects)

Table 14.2.2.1: Summary of Efficacy by Evaluation – Secondary Efficacy Variables (Full Analysis Set Subjects)

Table 14.2.2.2: Summary of Efficacy by Evaluation – Secondary Efficacy Variables (Per-Protocol Subjects)

Table 14.2.3.1.1: Pooling Analysis of the Co-Primary Efficacy Endpoints (Full Analysis Set Subjects)

Table 14.2.3.1.2: Summary of Co-Primary Efficacy Endpoints by Analysis Center (Full Analysis Set Subjects)

Table 14.2.3.2.1: Analysis of Co-Primary Efficacy Endpoints (Full Analysis Set Subjects)

Table 14.2.3.2.2: Analysis of Co-Primary Efficacy Endpoints (Per-Protocol Subjects)

Table 14.2.3.2.3: Sensitivity Analysis of Co-Primary Efficacy Endpoints (Full Analysis Set Subjects)

Table 14.2.3.3.1: Summary of Secondary Efficacy Endpoints (Full Analysis Set Subjects)

Table 14.2.3.3.2: Summary of Secondary Efficacy Endpoints (Per-Protocol Subjects)

Table 14.2.3.4: Summary of Co-Primary Efficacy Endpoints by Subgroups (Full Analysis Set Subjects)

Table 14.2.4: Summary of Procedure Information (Full Analysis Set Subjects)

Table 14.3.1.1.1: Summary of Treatment-Emergent Adverse Events (TEAEs) that Resulted in Discontinuation from the Study (Safety Subjects)

Table 14.3.1.2.1: Summary of Treatment-Emergent Adverse Event Characteristics by Time Period (Safety Subjects)

Table 14.3.1.2.2: Summary of Subjects Reporting Treatment-Emergent Adverse Events (TEAEs) by Time Period (Safety Subjects)

CONFIDENTIAL

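### In the deciding FAS analysis, LOCF can score as a bleeding success a woman who left for documented lack of efficacy, whom the SAP scores a failure only in the supportive PP analysis

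*SAP*

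**What the plan says.** SAP 5.6 ranks the two analyses: "FAS) will be considered primary. Analyses performed on the Per-Protocol (PP) will be secondary and supportive". Under SAP 5.6.1, a treated woman leaves the FAS only for pregnancy during the 12 months or for a diagnosis that undermines the bleeding assessment. Leaving for lack of efficacy is not an exclusion.

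For MBL, SAP 5.6.8.2 removes women who had surgical reintervention before 12 months. For everyone else the rule is: "Missing 12-month menstrual blood loss data will be imputed using last observation carried forward (LOCF").

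SAP 5.6.1 has a different rule in its PP definition. Women who stop because of a device- or procedure-related adverse event or "documented lack of efficacy (without surgical reintervention) will be included in the PP population, with missing data imputed as failure" for 12-month MBL. Nothing extends that rule to the FAS.

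On early exit, protocol 10.6 asks that "as many of the month 12 study procedures should be performed as possible at the time of withdrawal", and adds: "The Investigator shall complete a study exit case report form with as much information as is available at the time of withdrawal". It also says the investigator cannot insist on an exit visit. The SAP does not say whether an exit or baseline PBAC counts as the last observation.

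For sensitivity, SAP 5.6.8.2 says: "A worst-case analysis (all missing data imputed as failures) and best-case analysis (all missing data imputed as successes) will be performed". It adds a tipping-point analysis, and SAP section 6 lists Table 14.2.3.2.3, "Sensitivity Analysis of Co-Primary Efficacy Endpoints (Full Analysis Set Subjects").

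**The concern.** The SAP has already judged that documented lack of efficacy without reintervention is an MBL failure. It applies that judgement only in the analysis that does not decide the trial. In the analysis that does, the same woman is scored on her last diary. If she responded early, relapsed and left, that diary can be a success.

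Such diaries can exist. The protocol collects the PBAC at 3 and 6 months (Table 4 and section 12.3), and the SAP schedule (Table 2) at 6 months. This is a single-arm trial with a fixed 45% threshold, so no control group shares the error. Every misclassified woman moves the result towards success.

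**Working it through.** **Inputs.** The MBL criterion is a lower 95% exact limit of at least 45% (SAP 5.6.4.1, Table 3). The assumed success rate is 60%, with 125 women for 90% power (SAP 5.6.7, Table 4). The protocol plans 147 treated women (19.1). Sidedness of the interval is not stated; I take it as two-sided, with 2.5% in the lower tail. N = 147 is an upper limit for the MBL analysis, because women with reintervention or an FAS exclusion leave it.

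**The plan's own figure.** The critical count r is the smallest number of successes whose Clopper-Pearson lower limit is at least 0.45.

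| N | r | Limit at r | Limit at r − 1 | P(X ≥ r), rate 0.45 | P(X ≥ r), rate 0.60 |
|---|---|---|---|---|---|
| 125 | 68 | 0.4525 | 0.4446 | 2.2% | 91.4% |
| 147 | 79 | 0.4534 | 0.4466 | 2.1% | 94.8% |

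The stated 125 for 90% power reproduces. At the boundary, one woman scored success instead of failure decides the endpoint.

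**The path through the text.** Take a treated woman with no reintervention, no pregnancy, no interfering diagnosis, documented lack of efficacy, no usable exit PBAC, and a 6-month PBAC at least 50% below baseline and under 250.
- FAS: she is included, her 12-month value is missing, and LOCF carries the 6-month score. **Success.**
- PP: she is included by the readmission rule and imputed. **Failure.**

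**Effect on the chance of passing.** Let L be the share of analysed women who leave this way with 12-month MBL missing, and s the share of them whose last score qualifies. Neither is in the documents; both are assumptions. If the true rate is 45% with these women as failures, LOCF makes the scored rate 0.45 + L·s, and the chance of passing is P(Bin(N, 0.45 + L·s) ≥ r). For example, L = 5% and s = 0.2 give 0.45 + 0.01 = 0.46.

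| | None | L = 1% | L = 2% | L = 5% |
|---|---|---|---|---|
| N = 147, s = 0.2 | 2.1% | 2.3% | 2.6% | 3.6% |
| N = 147, s = 0.5 | 2.1% | 2.7% | 3.6% | 7.6% |
| N = 125, s = 0.2 | 2.2% | 2.4% | 2.7% | 3.7% |
| N = 125, s = 0.5 | 2.2% | 2.8% | 3.7% | 7.3% |

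L = 5% is about 7 of 147 women, a third of the planned 15% dropout. I regard s = 0.5 as high.

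**At the planning assumption.** 0.60 × 147 = 88.2 successes are expected against 79 needed, so the rule would matter only if results fell well short of plan.

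**Power cost of scoring failures.** Let m such women be present and 60% of the others succeed. With failure scoring, power is P(Bin(N − m, 0.60) ≥ r). Under LOCF with s = 0.2 it is P(Bin(N − m, 0.60) + Bin(m, 0.2) ≥ r).

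| | Failure scoring | LOCF, s = 0.2 |
|---|---|---|
| N = 147, m = 3 | 0.91 | 0.92 |
| N = 147, m = 5 | 0.87 | 0.90 |
| N = 125, m = 3 | 0.85 | 0.88 |
| N = 125, m = 5 | 0.80 | 0.84 |

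**The case against.** The best defence is that several conditions must coincide, that the exit procedures in protocol 10.6 would often supply a failing PBAC, and that the worst-case analysis is at least as strict as the proposed rule. All of that stands, and it limits the size. It does not close the gap. Exit procedures are done only as far as possible, the SAP does not say how an exit PBAC is used, and no sensitivity analysis decides study success.

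A second objection is that neither document defines lack of efficacy. Her complaint could concern another fibroid symptom, while her last diary met the endpoint's own criterion. That is fair, and the fix should supply a bleeding-based definition.

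A third is that women who had surgery leave the MBL denominator, so failing those who left without surgery would look uneven. That exclusion is a separate question and does not justify LOCF here.

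Four stronger readings are tempting but not supported:
- **A false-success risk near 11%.** That figure (10.8%) follows if 5 of 147 such women all have a qualifying last score. It is a ceiling for that count, not an estimate.
- **LOCF and failure imputation conflict within the PP.** They do not. SAP 5.6.1 removes women without a 12-month PBAC and readmits only those it scores as failures, so LOCF has nobody else to act on.
- **Women with no post-treatment diary drop out of the FAS denominator.** The SAP does not say so. Every eligible woman has a baseline PBAC, and carrying it forward gives failure. The text needs clarifying, but it does not support a computed bias.
- **Adverse-event leavers are also misclassified.** They are not known bleeding failures. Treatment is planned as one session ("The intent is for all clinically relevant fibroids to be ablated during a single treatment session"), so leaving afterwards says nothing by itself about bleeding. For them the FAS and PP rules differ without explanation, but neither is shown to be wrong.

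**Conclusion.** The point holds. For women who leave for documented lack of efficacy without reintervention, the deciding FAS analysis can be more lenient than the supportive PP analysis, against the SAP's own scoring of the same event.

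The size is probably small: with 147 women, a chance of passing at a true 45% of 2.3 to 3.6% instead of 2.1% if 20% of such women have a qualifying last score, and up to 7.6% at the high end of the assumed range. It is close to nil if exit PBACs are obtained, used, and fail. It matters near the boundary. The text is clear on the split; the size rests on assumed shares and on a two-sided interval. The change should be made, but the gap does not by itself undermine the primary analysis.

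**What to change.** In SAP 5.6.8.2:

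1. Apply the SAP 5.6.1 rule to the FAS: a woman who discontinues for documented lack of efficacy without surgical reintervention and has no 12-month PBAC is an MBL failure. Define lack of efficacy for this purpose as persistent or recurrent heavy menstrual bleeding, and fix the reason for discontinuation before database lock.
2. Limit LOCF to other missing cases.
3. State that an exit-visit PBAC counts as the last observation and that, with no post-treatment PBAC, baseline is carried forward (a failure). No woman then leaves the denominator for want of a score.
4. Optionally, prespecify failure scoring of device- or procedure-related adverse-event leavers in the FAS as a sensitivity analysis.

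The cost is a few sentences. An exit form is already required (protocol 10.6) and reasons for discontinuation are already to be summarised (SAP 5.6.2), although the exit form should be checked to confirm that it records the reason in usable form. The FAS success rate falls slightly, and power falls by about 1 to 4 percentage points in the cases tabulated. Women who withdraw without giving a reason, as protocol 10.6 allows, stay under LOCF, so the worst-case and tipping-point analyses should be kept.

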19.1 Sample Size

A. Reduction in Menstrual Blood Loss (MBL) at 12 months

Ho: Population proportion of MBL success < 0.45

Ha: Population proportion of MBL success ≥ 0.45

In order to claim study success for MBL, the lower limit of the 95% confidence interval must be ≥ 0.45 .

Under the assumption that the MBL success rate is at least 0.60, a sample size of 125 subjects provides better than 90% power to demonstrate that the lower limit of the 95% confidence interval exceeds the pre-specified threshold.

B. Rate of surgical re-intervention for HMB

Ho: Population proportion of no surgical re-intervention success < 0.75

Ha: Population proportion of no surgical re-intervention success ≥ 0.75

In order to claim study success for surgical re-intervention, the lower limit of the 95% confidence interval must be ≥ 0.75 . Under the assumption that the no surgical re-intervention success rate is at least 0.9, a sample size of 75 provides better than 90% power to demonstrate that the lower limit of the 95% confidence interval exceeds the pre-specified threshold.

C. Allowance for expected dropout rate

To account for an assumed 15% subject dropout rate (subjects lost to follow-up at the 12-month visit), a sample size of 147 treated subjects will be enrolled and treated.

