5.6.4.1 Primary Efficacy Analysis

Table 3 describes the two co-primary endpoints. Each subject will be determined to be a Success or Failure per the subject success criteria. For the endpoint of Reduction in Menstrual Blood Loss, the count and percentage of subjects with Success and Failure will be summarized, along with the 95% exact confidence interval for the percent successes. The rate of surgical reintervention during 12 months, along with 95% confidence interval, will be determined using Life-Table methods. Each endpoint has a pre-specified study success criterion, as described in Table 3. Study success is achieved if both of study success criteria are met.

Table 3: Co-Primary Endpoints and Success Criteria

Co-Primary Endpoint	Test Method	Subject Success Criteria ^a	Study Success Criteria
Reduction in MBL at 12 months	Modified pictorial blood loss assessment chart (PBAC)	≥ 50% reduction in PBAC score, and a final PBAC score < 250	LCL of the percentage of subject success ≥ 45%
Rate of surgical reintervention for HMB due to treatment failure at 12 months	Surgical reintervention for HMB due to treatment failure	No surgical reintervention for HMB due to treatment failure at 12 months	LCL of the percentage of subject success ≥ 75%

^a Subject success is calculated separately for the two co-primary endpoints, such that it is possible for a subject to be considered a success for one co-primary endpoint and not for the other.

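### The bleeding co-primary leaves out women reoperated before month 12, although the primary FAS keeps them, so the trial can pass when the FAS-wide lower limit is below 45%

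*SAP*

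**What the plan says.** - **Exclusion.** SAP 5.6.8.2, on MBL at 12 months: "Subjects which undergo surgical reintervention to manage fibroid symptoms prior to 12 months will be excluded from the Reduction in Menstrual Blood Loss analysis".
- **Primary population.** SAP 5.6 makes the FAS analysis primary: "FAS) will be considered primary. Analyses performed on the Per-Protocol (PP) will be secondary and supportive". SAP 5.6.1 defines the set: "The FAS population will be comprised of all study subjects who were treated and who do not meet any of the following criteria". The two criteria that follow are pregnancy within 12 months and a diagnosis that makes bleeding assessment invalid or unreliable. Reintervention is not among them.
- **Scoring.** SAP 5.6.4.1, and Protocol 19.3 in the same words: "Each subject will be determined to be a Success or Failure per the subject success criteria". MBL success needs at least a 50% fall in the PBAC score and a final score below 250. The study criterion is an exact 95% lower confidence limit (LCL) of at least 45%.
- **Hypothesis.** Protocol 19.1: "Ho: Population proportion of MBL success < 0.45". The population is not qualified further.
- **Second co-primary.** SAP Table 3 defines subject success as "No surgical reintervention for HMB due to treatment failure at 12 months", analysed by life-table methods with an LCL of at least 75%. The study succeeds only if both co-primaries are met. Sample size is set "Under the assumption that the no surgical re-intervention success rate is at least 0.9".
- **Per-protocol set.** SAP 5.6.1 says that subjects who discontinue for a device- or procedure-related adverse event or "documented lack of efficacy (without surgical reintervention) will be included in the PP population, with missing data imputed as failure" for the 12-month MBL endpoint.
- **Sensitivity analyses.** Worst-case, best-case and tipping-point analyses are planned for missing data (SAP 5.6.8.2) on the FAS (SAP 6, Table 14.2.3.2.3).

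**The concern.** A woman who needs further surgery for fibroid symptoms within a year will usually have responded poorly. Removing her takes a likely failure out of the denominator and leaves the numerator nearly untouched. The MBL table would carry the FAS label while omitting part of the FAS, and the omitted part is selected by outcome. In the supportive per-protocol set, by contrast, a woman who stops for lack of efficacy without surgery is scored as an MBL failure.

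The trial has one arm and is judged against a fixed 45% goal, so the choice of denominator can decide whether it passes. The plan does not state to which women the 45% goal and the assumed 60% apply.

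**Working it through.** **Inputs.** Goal 45%, assumed MBL success 60%, N = 125 (Protocol 19.1; SAP Table 4). Goal 75%, assumed freedom from reintervention at least 90%, N = 75 (same places). 147 treated (Protocol 19.1). Exact two-sided 95% interval for MBL (SAP 5.6.4.1). Reintervention rates of 1%, 2% and 5% are assumptions. 10% is the highest rate that the plan's own assumption allows (1 - 0.90).

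**The plan's figures reproduce.** The pass mark is the smallest x for which the Clopper-Pearson lower limit of x/n reaches the goal.
- MBL, n = 125: pass mark 68 (LCL 45.25%); P(Bin(125, 0.60) ≥ 68) = 91.4%.
- Reintervention, n = 75: pass mark 64; P(Bin(75, 0.90) ≥ 64) = 93.1%.

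**Inflation of the rate.** With k of N women excluded and x successes, the reported rate is x/(N - k) and the FAS-wide rate, with reintervention as failure, is x/N. Their ratio is N/(N - k) = 1/(1 - k/N). For k = 15 this is 147/132 = 1.11.

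**Results that pass although the FAS-wide LCL is below 45% (N = 147).** With reintervention scored as failure, the pass mark is fixed at 79/147 (LCL 45.3%).

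| Excluded (k) | SAP rule | LCL | FAS-wide | LCL |
|---|---|---|---|---|
| 2 | 78/145 | 45.3% | 78/147 | 44.7% |
| 7 | 76/140 | 45.7% | 76/147 | 43.3% |
| 15 | 72/132 | 45.7% | 72/147 | 40.7% |
| 26 | 66/121 | 45.2% | 66/147 | 36.7% |

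The discrepancy cannot occur with 0 or 1 exclusion.

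**Does the second co-primary stop this?** By the exact limit, 121/147 free of reintervention gives LCL 75.2% and 120/147 gives 74.4%. It therefore tolerates 147 - 121 = 26 reinterventions, so every row above can occur in a trial that passes both.

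**Chance of meeting both co-primaries at a true 45% (N = 147).** Let r be the reintervention rate and c(n) the MBL pass mark for n women. If the FAS-wide success rate is 0.45, the rate among women not reoperated is 0.45/(1 - r). Then

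P = Σ over k = 0 to 26 of P(Bin(147, r) = k) × P(Bin(147 - k, 0.45/(1 - r)) ≥ c(147 - k)).

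Scoring reintervention as failure replaces c(147 - k) by 79. Reading the goal as one for non-reintervened women replaces 0.45/(1 - r) by 0.45.

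| r | SAP rule, goal for whole FAS | Reintervention as failure | SAP rule, goal for non-reintervened women |
|---|---|---|---|
| 0% | 2.1% | 2.1% | 2.1% |
| 1% | 2.46% | 2.1% | 1.9% |
| 2% | 3.2% | 2.1% | 1.9% |
| 5% | 6.5% | 2.1% | 1.9% |
| 10% | 18.1% | 2.1% | 1.9% |

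The reference is 2.5%, the lower tail of a two-sided 95% interval. At 1% there is no excess over it.

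**Power with reintervention as failure, N = 147.** If 60% is the FAS-wide rate: P(Bin(147, 0.60) ≥ 79) = 94.8%. If 60% applies only to women not reoperated, the FAS-wide rate is 0.60(1 - r). At r = 5% it is 57% and power is 81.1%; at r = 10% it is 54% and power is 55.9%.

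**Assumptions.** Full follow-up; every excluded woman counts on the second co-primary; the exact binomial limit stands in for the life-table interval, whose form the SAP does not name. If only half of the excluded women count on the second co-primary, the rounded SAP-rule results at 1%, 2%, 5% and 10% do not change.

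**The case against.** **The rule is prespecified and specific.** SAP 5.6.8.2 states who enters the MBL analysis, and a specific rule can stand beside a general population definition. A reader might infer a flat contradiction between the exclusion and the FAS. The documents do not support that: no passage says that a reoperated woman is an MBL failure, and the MBL criterion rests on a PBAC score that surgery makes uninterpretable. What stands is an outcome-related denominator that the plan has not reconciled with its primary population.

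**The error rate depends on the target.** A reader might infer that the false-positive rate of this trial is 18.1%. It is not shown to be. That figure needs the 45% goal to apply to the whole FAS with reintervention as failure, and it needs the highest reintervention rate that the plan's assumption allows. If the goal concerns non-reintervened women, as 5.6.8.2 can be read, the chance is 1.9-2.1%.

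**Reoperation has its own co-primary.** This is a real safeguard, since both must be met, but a partial one. It tolerates 26 of 147. It also counts only surgery for heavy bleeding due to treatment failure, whereas the exclusion covers surgery for any fibroid symptom. A woman reoperated for another fibroid symptom could leave the MBL analysis and fail neither endpoint.

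**Sensitivity analyses exist.** They may include these women, but the SAP does not say whether an excluded woman counts as missing, and they do not enter the success rule.

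**The exclusion has a sound purpose.** It keeps a PBAC score taken after, say, a hysterectomy from counting as treatment success. Any change must keep that protection.

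**Conclusion.** The concern holds as an unreconciled, outcome-related denominator in a co-primary analysis, and it should be fixed. The reported MBL rate exceeds the FAS-wide rate by 1/(1 - reintervention rate). From two reinterventions onward the trial can pass with an FAS-wide LCL below 45%. The gap is marginal at two (45.3% against 44.7%) and 5 percentage points at 15 (45.7% against 40.7%).

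Inflated error is a conditional finding. If the goal is for the whole FAS, the chance of passing both co-primaries at a true 45% is 3.2% at 2% reintervention, 6.5% at 5% and 18.1% at 10%, with no excess at 1%. If the goal is for non-reintervened women only, there is no excess at any of these rates, but the primary result then describes a subset chosen by outcome, and the plan does not say that this is intended. The lower limits in the first table need only the counts shown; the probabilities rest on the assumptions listed with the calculation.

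**What to change.** **SAP 5.6.8.2.** In the primary FAS analysis of MBL, count women with surgical reintervention before 12 months as failures. Use no PBAC score obtained after the surgery and carry no earlier score forward for them. Keep them as failures in the worst-case, best-case and tipping-point analyses. Retain the analysis that excludes them as supportive.

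**Trigger wording.** Reconcile the exclusion's reference to fibroid symptoms with the second co-primary's reference to heavy bleeding due to treatment failure. Add a sensitivity analysis in which women operated on only for a non-bleeding fibroid symptom are scored on their last PBAC before surgery. The second co-primary itself need not change.

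**SAP 5.6.7.** State that the 45% goal and the assumed 60% refer to all FAS women on this basis. If 60% was meant for women not reoperated, restate the power.

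**Cost.** No new data are needed. The MBL rate becomes less favourable, and in the primary analysis a woman operated on for a non-bleeding symptom may count as a bleeding failure, which is why the sensitivity analysis is needed. The change touches an endpoint, so it may need amendment review under Protocol 16.2. On the FAS-wide reading of 60%, power at N = 147 is 94.8% and the sample size is unaffected. On the other reading the cost is real: 90% power would take about 189 women at 5% reintervention (57% success) and about 340 at 10% (54% success), before any allowance for dropout.
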